7.5. Non-Multiplicity Adjusted Secondary Efficacy Variable and Analysis

Other non-multiplicity adjusted secondary efficacy variables are listed and defined in Sections 2 and 3.2.3.

For all Q-Motor analyses [REDACTED]

[REDACTED] Analysis of Q-Motor [REDACTED]

For continuous variables, an MMRM model as described in Section 7.2 for the primary endpoint in mITT population will be used, with Baseline value of the analyzed variable replacing Baseline UHDRS-TFC as a covariate. For the specified visits, the LSMs, SE of the estimates, p-values, and 2-sided 95% CIs will be provided for the within treatment group changes from Baseline and for the comparison of change from Baseline between pridopidine and placebo. This will be repeated in W65PP or W78PP population depending on whether change to Week 65 or 78 is analyzed.

In addition, actual values and changes from Baseline to each visit will be summarized using descriptive statistics for each endpoint. The sub-scale scores of each endpoint will also be summarized where applicable.

The proportion of responders will be analyzed in a similar way to how the binary UHDRS-TFC response is analyzed for the main estimand and Supportive Estimand 1. Different thresholds than specified above may be explored. Descriptive statistics and 95% CI using normal approximation will be provided for the proportions at each visit. In order to minimize impact of outliers that may represent unrealistic changes in key endpoints, analyses using robust regression or other methods may be performed.

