		(Section 7.3.3) Added text to conduct additional exploratory analysis to explore impact of confounding factors. Added sensitivity analysis on neuroleptic use.	Since use of neuroleptics may impact efficacy and was a stratification factor in the study a sensitivity analysis on its use was added.
		(Section 7.4.2) updated that CI's for observed proportions and the difference will be provided using Clopper-Pearson method.	Since it provides the exact CI for observed proportions.
		(Section 7.4.3) Subgroup analyses will be performed on log2-transformed NfL.	To better understand changes in NfL for the different subgroups.
		(Section 7.5) Additional analyses on Q-Motor adjusting for covariates that may impact it were included.	Since Age, Sex and Weight can impact Q-Motor assessments these were added as covariates that may be explored for impact on efficacy.
		(Section 7.5) Added text on robust regression or other analyses.	In order to minimize the impact of outliers that may represent unrealistic changes in key endpoints, text on analyses using robust regression or other methods was added.
		(Section 7.6) Additional analyses may be performed based on subgroups of baseline PIN _{HD} values	In order to understand impact of PIN _{HD} on efficacy.
		(Section 7.6) Additional analyses may be performed on change from baseline in Weight	In order to evaluate changes in weight
		(Section 8.2) Inequality signs updated for analysis of duration of exposure.	Inequality signs were made consistent between interval and cumulative thresholds.
		(Section 8.3) Additional details added on calculation of Compliance and display of relevant data in Listings. Ranges for	Due to participants sometimes not returning bottles additional details

SAP Version	Approval Date	Change	Rationale
		compliance were updated to better reflect range of compliance.	on handling this were added.
		(Section 8.4) Updated to reflect that AEs that start more than 14 days after the end of treatment are not considered TEAEs.	Due to the short half-life of Pridopidine AEs that started more than 14 days after the end of treatment were not considered TEAEs.
		(Section 8.4 and Appendix 12.2) Analyses of Abuse Potential was added.	Analyses of Abuse Potential were deemed important and added.
		(Section 8.6) Criteria for detection of clinically significant laboratory abnormalities were updated.	Updated to be consistent with Laboratory Nonnal Ranges.

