3.2.2. Multiplicity-adjusted Secondary Efficacy Endpoints

The key secondary efficacy endpoint for this study is:

- change from Baseline to Week 65 in cUHDRS total score

The other multiplicity-adjusted secondary efficacy endpoints for this study are to evaluate the efficacy of pridopidine 45 mg bid vs. placebo as measured by:

- the proportion of participants with improvement or no worsening in UHDRS-TFC at Week 65 (change from Baseline \geq 0 points) using responder analysis
- change from Baseline to Week 52 in UHDRS-TFC score
- change from Baseline to Week 78 in UHDRS-TFC score
- change from Baseline to Week 65 in Q-Motor [REDACTED]
[REDACTED]

- change from Baseline to Week 65 in UHDRS-TMS (defined as the sum of all UHDRS motor domains ratings)
- change from Baseline to Week 65 in SDMT score
- change from Baseline to Week 52 in UHDRS-TMS score
- proportion of participants with no change or improvement in CGI-C at Week 65

For responder analyses where there are fewer than 5 responders (overall between both treatment groups), the analyses will not be performed as too few responders will not allow for comparison of responders between treated and placebo participants.

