3.2.3. Non-multiplicity Adjusted Secondary Efficacy Endpoints

The non-multiplicity adjusted secondary efficacy endpoints (listed in Section 2) will evaluate the efficacy of pridopidine 45 mg bid vs. placebo, as measured by change from Baseline to post-baseline scheduled visits in UHDRS-TFC (total score and subscales), cUHDRS, UHDRS-TMS (total score and subscales), dystonia score for those participants with severe dystonia at Baseline (defined as UHDRS-TMS-dystonia score ≥ 4), SDMT, SWR, Q-Motor measurements [REDACTED] at Weeks [REDACTED]

26, 39, 52, 65 and 78, if not presented as primary or multiplicity-adjusted secondary endpoints.

The proportion of participants with response in cUHDRS, UHDRS-TMS, Q-Motor [REDACTED] [REDACTED], and CGI-C at Weeks 26, 39 (not for Q-Motor assessments), 52, 65 and 78, if not presented as primary and multiplicity-adjusted secondary endpoints, will also be evaluated as non-multiplicity adjusted secondary efficacy endpoints. The response in each endpoint is defined as follows:

- Improvement or no worsening in Q-Motor [REDACTED] with change from Baseline ≤ 0 at corresponding post-baseline visit
- Improvement or no worsening in UHDRS-TMS with change from Baseline ≤ 0 at corresponding post-baseline visits
- Change from Baseline in cUHDRS ≥ -1 at corresponding post-baseline visits
- Response in CGI-C defined using different thresholds (i.e., 1, 1 to 2, 1 to 3, 1 to 4) at corresponding post-baseline visits

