The odds ratio (OR) of treatment effect (pridopidine 45 mg bid vs placebo) along with a 2-sided 95% CI and p-value will be presented. An estimate of OR > 1 will indicate a beneficial treatment effect. Descriptive statistics and 95% CI using Clopper-Pearson will be provided for the observed proportions at each visit, along with the difference between treatment groups in the proportions and 95% normally approximated CI for the difference.

Following supportive estimands will be used to support the analysis of this secondary endpoint:

Supportive Estimand 1: similarly defined as the main estimand for UHDRS-TFC responder analysis, but with population changed to ITT population, and MNAR instead of MAR MI will be used under the hypothetical strategy.

Supportive Estimand 2: similarly defined as the main estimand for UHDRS-TFC responder analysis, but with population changed to ITT population.

Supportive Estimand 3: similarly defined as the main estimand for UHDRS-TFC responder analysis, but with ICE handling strategy changed to treatment policy strategy (using observed data without imputation).

Supportive Estimand 4: similarly defined as Supportive Estimand 3 for UHDRS-TFC responder analysis, but with population changed to W65PP population.

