12.1.5.2. Clinical Global Impression – Change (CGI-C)

The CGI-C scale measures the change in the participant's clinical status from a specific point in time, using a 7-point scale, ranging from 1 (very much improved) to 7 (very much worse), with a score of 4 indicating no change.

Responder analyses will be performed at Week 65 as a secondary efficacy endpoint with analysis at all other post-baseline visits as additional efficacy analyses. Responder analyses comparing participants randomized to pridopidine vs placebo will be performed using CGI-C for those:

- (a) who have no change or improve (Scores of 1,2,3 or 4)
- (b) who Minimally or more improved (Scores of 1,2, or 3)
- (c) who Are Much or Very Much improved (Scores of 1 or 2)
- (d) who are Very Much improved (Score of 1)

Description	Score
Not assessed	0
Very Much Improved	1
Much Improved	2
Minimally improved	3
No change	4
Minimally worse	5
Much worse	6
Very much worse	7

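### SAP 7.5 uses normal-approximation intervals for responder proportions that may be rare, while SAP 7.4.2 uses Clopper-Pearson for observed responder proportions

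*SAP*

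**What the plan says.** SAP 7.5 covers the responder endpoints outside the testing hierarchy. On intervals it says: "Descriptive statistics and 95% CI using normal approximation will be provided for the proportions at each visit".

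SAP 7.4.2, for UHDRS-TFC response, says: "Descriptive statistics and 95% CI using Clopper-Pearson will be provided for the observed proportions at each visit". The revision table for SAP version 3.0 explains that choice: "Since it provides the exact CI for observed proportions". For the between-arm difference, 7.4.2 keeps a normal approximation: "along with the difference between treatment groups in the proportions and 95% normally approximated CI for the difference".

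The CGI-C endpoints under 7.5 are set in SAP 3.2.3: "Response in CGI-C defined using different thresholds (i.e., 1, 1 to 2, 1 to 3, 1 to 4) at corresponding post-baseline visits". SAP 12.1.5.2 shows that score 1 is the very-much-improved category and that 1 to 2 adds much improved.

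SAP 3.2.2 sets a minimum count: "For responder analyses where there are fewer than 5 responders (overall between both treatment groups), the analyses will not be performed". It stands in the section on multiplicity-adjusted endpoints but is worded for responder analyses in general.

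Arms are compared by model. SAP 7.5 says: "The proportion of responders will be analyzed in a similar way to how the binary UHDRS-TFC response is analyzed", which means logistic regression with an odds ratio.

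**The concern.** The two sections name different interval methods for single-arm responder proportions by visit, and the reason given for the exact method in 7.4.2 applies equally to 7.5. The allocation also looks the wrong way round. UHDRS-TFC response (no worsening) is unlikely to be near zero, and there the normal approximation would do. The strict CGI-C thresholds in 7.5 could be near zero in a disease whose functional capacity the protocol (8.1.1) describes as declining throughout, and there the approximation can fail.

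What is at stake is the credibility of some table entries: an interval of zero width, a negative lower limit, or an interval labelled 95% that covers less often than that.

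**Working it through.** **Inputs.** Planned arm size is 480/2 = 240 (SAP 3.1). The SAP 3.0 revision table reports 499 randomized, about 250 per arm. Nominal coverage is 95%. Neither document gives an expected CGI-C response rate or a coverage figure, so there is no plan figure to reproduce, and every true rate below is an assumption.

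**Step 1: printed intervals, with no assumed rate.** For x responders among n = 240, the normal interval is x/n ± 1.96·√[(x/n)(1 − x/n)/n].

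| Responders | Normal approximation | Clopper-Pearson |
|---|---|---|
| 0 | 0% to 0% | 0% to 1.53% |
| 1 | −0.40% to 1.23% | 0.01% to 2.30% |
| 2 | −0.32% to 1.98% | 0.10% to 2.98% |
| 3 | −0.16% to 2.66% | 0.26% to 3.61% |
| 5 | 0.28% to 3.89% | 0.68% to 4.79% |

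**Step 2: does the fewer-than-5 rule prevent these?** No. It counts both arms, so 0 versus 5, or 3 versus 2, passes and the small arm's interval is printed.

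**Step 3: exact coverage at an assumed true rate p.** Coverage is the sum of Binomial(240, p) probabilities over every x whose interval contains p. At p = 1.25%, the interval contains p only for x = 2 to 8: 0.2245 + 0.2255 + 0.1691 + 0.1010 + 0.0501 + 0.0212 + 0.0078 = 0.799. With x = 1 it just misses, because the upper limit is 1.23%. At p = 1%, x = 1 is included and coverage rises to 91%. This is why coverage oscillates.

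**Step 4: the same, given that the rule lets the analysis run.** Let X ~ Bin(240, p) be this arm and Y ~ Bin(240, kp) the other. Weight each x by P(X = x)·P(Y ≥ 5 − x) and divide by the sum of the weights. Use k = 1 for equal rates and k = 2 for twice the rate in the other arm.

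| True rate | Normal, no rule | Normal, rule, k = 1 | Normal, rule, k = 2 | Clopper-Pearson, no rule |
|---|---|---|---|---|
| 1% | 91% | 98% | 94% | 99% |
| 1.25% | 80% | 91% | 83% | 99% |
| 1.5% | 87% | 93% | 88% | 99% |
| 2% | 86% | 88% | 86% | 97% |
| 2.5% | 93% | 94% | 93% | 96% |
| 10% | 94% | 94% | 94% | 96% |
| 30% | 95% | 95% | 95% | 96% |

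Over all rates from 1% to 2%, coverage without the rule runs from about 79% to 95%, with a mean of 89.6%. At 250 per arm, coverage without the rule at 1.25%, 1.5% and 2% is 81.6%, 88.5% and 87.3%, so actual enrolment does not change the picture.

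**Step 5: how much the rule removes.** With equal rates it drops the analysis in 1 − 0.524 = 48% of trials at 1% and in 1 − 0.717 = 28% at 1.25%. Where the analysis runs at 1.25%, this arm's lower limit is still at or below zero in 52% of trials with equal rates and 63% with the other arm at twice the rate.

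**The case against.** **The size depends on a rate nobody has stated.** A reader might infer that these intervals actually cover 80% to 88% of the time. The documents do not support that. It holds only at particular assumed rates between 1.25% and 2%; coverage is 91% at 1% and 93% at 2.5%, before the rule is applied. This objection stands, and the size can be given only as conditional.

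**The fewer-than-5 rule removes many of the worst cases.** With equal arms it raises coverage at 1.25% from 80% to 91%. It helps less when the arms differ and does not prevent the zero-width or negative intervals in Step 1. This objection stands in part.

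**Most 7.5 endpoints are probably unaffected.** A reader might infer that the 7.5 intervals are too narrow in general. Only CGI-C thresholds 1 and 1 to 2 are plausibly rare. Nothing in the documents suggests that the TMS, cUHDRS, Q-Motor or wider CGI-C responses are, and for common responses coverage is near nominal.

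**No inference depends on these intervals.** This is correct. Arms are compared by odds ratio, and the endpoints lie outside the hierarchy in SAP 5.6. A reading that they threaten a trial conclusion has no support.

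**The two sections may not mean the same quantity.** SAP 7.4.2 says observed proportions; 7.5 says only proportions, just after referring to estimands that use multiple imputation. Clopper-Pearson does not apply directly to pooled, non-integer counts. The mention of descriptive statistics points to observed data, but the text is ambiguous and the fix should say which is meant.

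**Should differences also get a score interval?** A reader might infer so. SAP 7.5 specifies no interval for a difference, and 7.4.2 uses a normal approximation for its own, so adding one in 7.5 alone would create a new mismatch.

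**Conclusion.** The point holds as a minor one. The difference between 7.5 and 7.4.2 is on the page and unexplained. The defect in the printed intervals at 0 to 3 responders in an arm follows from arithmetic at n = 240, and the minimum-responder rule leaves it possible.

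The coverage loss is conditional. It needs a true rate of roughly 1% to 2% in an arm, which the documents neither state nor rule out, and its size within that range depends on the exact rate and on the other arm's rate. The figures also assume about 240 participants with observed data per arm, and that the rule in 3.2.2 applies to 7.5. If it does not, the figures without the rule apply.

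**What to change.** In SAP 7.5, replace *using normal approximation* with *using Clopper-Pearson for the observed proportions*, as in 7.4.2. This aligns the two sections, removes zero-width and negative intervals, and makes clear that the descriptive interval refers to observed rather than imputed data. No change is proposed for intervals on differences.

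The cost is one phrase, and 7.4.2 already requires the method to be programmed. The downside is slightly conservative intervals: at 240 per arm, exact coverage is about 97% to 99% for true rates of 1% to 2%, and about 96% at 10%.

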7.6. Other Exploratory Efficacy Variable and Analyses

Other exploratory efficacy variables include:

- Change from Baseline to Weeks 26, 52, 65 and 78 in PBA-s domains subscale scores and total scores
- Change from Baseline to Weeks 26, 52, 65 and 78 in HDQoL

These will be analyzed similar as described in Section 7.5 for non-multiplicity adjusted secondary efficacy variables in their main estimand.

Responder analyses for select efficacy endpoints, such as UHDRS-TFC and cUHDRS, using clinically meaningful thresholds may be performed.

In addition, the observed virtual UHDRS-TFC assessments at virtual Baseline, Weeks 13, 32, and 58 and change from virtual Baseline (Day -7 Visit) at each post-baseline virtual visit will be summarized.

The impact of PIN_{HD}, defined as prognostic index normed for HD, on treatment effects for select efficacy variables may be explored using categorized PIN_{HD} score, where PIN_{HD} = (PI_{HD} - 883) / 1044, and PI_{HD} = 51 × TMS + (-34) × SDMT + 7 × Age × (CAG - 34), defined as prognostic index for HD (10).

Treatment effect on change from Baseline in weight over visits may also be explored adjusting for sex and age.

7.7. OLE Efficacy Analyses

The final analyses of OLE data will be performed at the End of OLE when all participants complete the OLE EoS visit. Interim analyses may be performed as needed.

The OLE analysis will be presented using the following labels for treatment group, in the order displayed:

- Placebo bid (Main Study) to Pridopidine 45 mg bid (OLE)
- Pridopidine 45 mg bid (Main Study) to Pridopidine 45 mg bid (OLE)
- Total of above two groups (where applicable)

Proportion of participants with change of UHDRS-TFC from Main Study Baseline ≥ -1 by treatment group and the difference between treatment groups at each OLE visit will be provided along with a 2-sided 95% CIs using normal approximation and p-values from a logistic regression similar to that described in Section 7.4.1. This analysis will be repeated using a threshold of 0 for proportion of participants with change of UHDRS-TFC from Main Study Baseline ≥ 0 .

Summary statistics will be presented for UHDRS-TFC, cUHDRS, UHDRS-TMS, Q-Motor

[REDACTED] and Q-Motor [REDACTED]

[REDACTED] by treatment group and visit during the OLE period as described below:

- Change from Main Study Baseline and the observed values of UHDRS-TFC, cUHDRS, UHDRS-TMS, and Q-Motor measurements at each OLE visit
- Change from OLE Baseline and the observed values of UHDRS-TFC, cUHDRS, UHDRS-TMS, and Q-Motor measurements at each OLE visit

In addition, the durability of treatment response to pridopidine in the OLE period will be assessed by the proportion of participants who continue to respond to pridopidine in OLE among the responders in double-blind treatment period. Responders defined using following endpoints will be assessed for the durability:

- Change from Main Study Baseline to Week 65 in UHDRS-TFC ≥ 0 , and change from Main Study Baseline to each OLE visit in UHDRS-TFC ≥ -1
- Change from Main Study Baseline to Week 65 in UHDRS-TFC ≥ 0 , and change from Main Study Baseline to each OLE visit in UHDRS-TFC or ≥ 0
- Change from Main Study Baseline to Week 65 in cUHDRS ≥ -1 , and change from Main Study Baseline to each OLE visit in cUHDRS ≥ -1.5

- Change from Main Study Baseline ≤ 0 in UHDRS-TMS at Week 65, and change from Main Study Baseline ≤ 0 in UHDRS-TMS at each OLE visit
- Change from Main Study Baseline ≤ 0 in Q-Motor [REDACTED] and change from Main Study Baseline ≤ 0 insec in Q-Motor [REDACTED] at each OLE visit

The Kaplan-Meier curve will be used to display by treatment group the distribution of time to first UHDRS-TFC worsening, defined as change from Main Study Baseline <-1 , and no further UHDRS-TFC response (i.e. change from Main Study Baseline ≥ -1) at subsequent visits after first UHDRS-TFC worsening. Time to first UHDRS-TFC worsening will be censored at the last available assessment in the OLE period if UHDRS-TFC worsening is not observed. Cox proportional hazards model will also be used to quantify the treatment difference in time to first UHDRS-TFC worsening with treatment group, region, and randomization stratification factors (HD stage and neuroleptic drug use) as the fixed effects. Hazard ratio of pridopidine vs placebo group will be displayed with 95% CI and p-value.

Other responder analyses for select efficacy endpoints in OLE period using clinically meaningful thresholds may be performed.

For pridopidine-to-pridopidine group in OLE mITT population, summary statistics will be presented for the observed values and change from Main Study Baseline in UHDRS-TFC, UHDRS-TMS, Q-Motor [REDACTED], and Q-Motor [REDACTED] in both double-blind and OLE periods. An MMRM model as described in Section 7.2 excluding treatment and treatment-by-visit effects will be used to fit the change from Main Study Baseline in these efficacy endpoints throughout Main Study and OLE Treatment Period. The LSM and 95% CI at each visit will be presented.

For placebo-to-pridopidine group in OLE mITT population, an MMRM model for Change from Main Study Baseline in UHDRS-TFC at each visit post Main Study Day 1 through Main Study and OLE periods will be used to estimate the gained treatment effect after switching to pridopidine treatment. The model will include fixed effects of treatment at each period (Main Study and OLE Treatment Period), randomization stratification factors (HD stage and neuroleptic drug use), categorical effects of study visit within each period (e.g., 26 weeks and 52 weeks within each period), interaction of treatment and visit within the period, and Main Study Baseline of UHDRS-TFC. The covariance structure for the MMRM model will be used similarly as described in Section 7.2. Mean difference in treatment effect at every 26 weeks receiving pridopidine 45 mg bid vs placebo will be presented along with 95% CIs and p-values.

For the exploratory endpoints in OLE, including CGI-C, PBA-s, HDQoL, SDMT, and SWR, the summary tables of observed values and change from Baseline over time will be provided by treatment group and OLE visit.

No imputation will be performed for the OLE analyses. Analyses using external controls may be performed to contextualize the long-term effect of pridopidine on treating HD in OLE period. These analyses, if required, will be detailed in a separate SAP.

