1.3.2. Schedule of Activities – Open-label Extension (OLE)

Table 3: Schedule of Activities – Open-label Extension

Study Period Procedures and assessments	Open-Label Titration Period		Open-Label Full-dose Treatment Period					Followup Safety Assessment	
	OLE V1 ^a (same as Main Study V8)		OLE V2		OLE V3		OLE V4+ ^b	OLE EoS /ET ^b	OLEF/U
Study Clinic Visit									
Telephone Call Safety Visit		📞		📞		📞			📞
OLE Study Week	OLE Day 1 (same as Main Study Wk 78/EoS)	OLE Wk 2	OLE Wk 4	OLE Wk 13	OLE Wk 26	OLE Wk 39 & every 26 wks thereafter	OLE Wk 52 & every 26 wks thereafter	X	+2 weeks after OLE EoS/ET
Visit Windows (days)		±1	±5	±5	±14	±14	±14	±14	±5
OLE Informed consent	X (if not obtained at Main Study V7)								
Re-confirm eligibility to OLE	X								
Clinical laboratory tests (serum chemistry, hematology) ^d	X		X		X		X	X	
Urinalysis ^e	X								
Pregnancy test (for WOCBP)	U		U		U		U	U	
	Monthly urine pregnancy test (at home)								
Brief physical examination	X (full PE)		X		X		X	X	
12 lead ECG	X ^{f,g}		X ^g		X ^h			X ^h	
Vital signs	X		X		X		X	X	
C-SSRS (since last visit version)	X		X	X	X	X	X	X	X
UHDRS-IFC	X				X		X	X	
UHDRS-TMS	X				X		X	X	
SDMT	X				X		X	X	
SWR	X				X		X	X	
Motor	X		X		X		X	X	
PBA-S (Short Form)	X		X		X	X	X	X	X
CGI-C	X				X		X	X	
HDQoL	X				X		X	X	

Prilenia Therapeutics

Study drug: Pridopidine
Protocol Number: PL101-HD301

Study Period Procedures and assessments	Open-Label Titration Period		Open-Label Full-dose Treatment Period					Follow-up Safety Assessment	
	OLE V1 ^a (same as Main Study V8)		OLEV2		OLE V3		OLEV4+ ^b	OLE EoS /ET ^b	OLEF/U
Study Clinic Visit									
Telephone Call Safety Visit		📞		📞		📞			📞
OLE Study Week	OLE Day 1 (same as Main Study Wk 78/EoS)	OLE Wk 2	OLE Wk 4	OLE Wk 13	OLE Wk 26	OLE Wk 39 & every 26 wks thereafter	OLE Wk 52 & every 26 wks thereafter	X	+2 weeks after OLE EoS/ET
Visit Windows (days)		±1	±5	±5	±14	±14	±14	±14	±5
Benzodiazepines and antidepressants inquiry	X	X	X	X	X	X	X	X	X
Alcohol/illicit drug use inquiry	X	X	X	X	X	X	X	X	X
Dispense/collect study drug	X		X		X		X	X (collect only)	
Review study compliance and adherence	X	X	X	X	X	X	X	X	X
Study drug administration	<=====X=====>								
Adverse event inquiry	X	X	X	X	X	X	X	X	X
Concomitant medication inquiry	X	X	X	X	X	X	X	X	X
Plasma sample for biomarkers analysis					X ^c		X	X ^c	

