Abbreviations: Clinical Global Impression of Change (CGI-C); Columbia-Suicide Severity Rating Scale (C-SSRS); electrocardiogram (ECG); End of Study (EoS); Early Termination (ET); Follow-up (F/U); Huntington Disease Quality of Life Questionnaire (HDQoL); Open-label Extension (OLE); Physical Examination (PE); Problem Behaviors Assessment—Short Form (PBA-s); Symbol Digit Modalities Test (SDMT); Stroop Word Reading (SWR); Total Functional Capacity (TFC); Total Motor Score (TMS); Unified Huntington Disease Rating Scale (UHDRS); Visit (V); women of childbearing potential (W●CBP).

Table Footnotes:

[figure not shown]
[figure not shown]
- The OLE VI is the same as Main Study V8 (or V7/W65 for the last group of participants in the Main Study). Assessments do not need to be repeated if conducted as part of the Main Study.
- A participant who discontinues study drug at any point during the OLE, must also be withdrawn from the study and attend an EoS visit.
- In-clinic visit window can be expanded to ±28 days; this applies to all in-clinic visits including OLE V1-4+ and OLE F/U. The expansion of the in-clinic visit window is only in case of a global pandemic.
- Collect blood after ECG is administered (not before).
- Urinalysis will be done as part of Main Study V8, not as part of OLE
- Triple ECG pre-dose.
- Single ECG 1-2 hours post-dose.
- Single ECG pre-dose.

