5.5. Derivation and Transformation on Data

5.5.1. Baseline Values

Two baselines (Main Study and OLE baselines) are defined as below. Both baselines can be used to analyze data collected during OLE period. Only Main Study Baseline will be used to analyze data collected during Main Study portion.

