5.5.1.2. OLE Baseline

OLE Baseline is defined as the last non-missing observed data prior to the first dose of pridopidine in the OLE period. In general, the OLE Baseline will be the OLE Day 1 assessment. For ECGs, the OLE Baseline value is the average of the 3 (triplicates) ECGs performed at OLE Day 1 visit before first drug administration.

Change from Baseline analysis of ECGs will be performed using Main Study or OLE Baseline as appropriate.

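### SAP 7.7 does not state the contrast for the gain after switching from placebo; the same-week contrast its terms suggest would include the decline on placebo before rollover

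*SAP*

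**What the plan says.** SAP 7.7 fits one model to the placebo-to-pridopidine group of the OLE mITT population. It is an "MMRM model for Change from Main Study Baseline in UHDRS-TFC at each visit post Main Study Day 1 through Main Study and OLE periods", and it "will be used to estimate the gained treatment effect after switching to pridopidine treatment". The fixed effects are treatment in each period, the stratification factors, Main Study Baseline TFC, "categorical effects of study visit within each period (e.g., 26 weeks and 52 weeks within each period"), and the treatment-by-visit interaction within period. The only sentence on the output is: "Mean difference in treatment effect at every 26 weeks receiving pridopidine 45 mg bid vs placebo will be presented along with 95% CIs and p-values". No contrast coefficients or reference visit are given. Protocol 9.4.6 describes the same model and adds nothing on the contrast.

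The SAP does define a second starting point. Section 5.5.1 says "Both baselines can be used to analyze data collected during OLE period", and 5.5.1.2 says "OLE Baseline is defined as the last non-missing observed data prior to the first dose of pridopidine in the OLE period". SAP 7.7 uses that baseline for descriptive summaries of TFC at OLE visits, but not for this model.

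**The concern.** The model is fitted to one group that receives placebo first and pridopidine later, so treatment and period coincide completely. No term in the model can separate them; what the analysis estimates depends entirely on which least-squares means are subtracted.

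The response is measured from Main Study Baseline throughout, and visits restart in each period. A pridopidine-versus-placebo difference at a given number of weeks on treatment then most naturally pairs OLE week 26 with Main Study week 26, and week 52 with week 52. The OLE mean in each pair carries everything lost on placebo since randomization; the Main Study mean carries only the first 26 or 52 weeks. In a disease with steady functional decline, that difference measures mainly elapsed time.

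At stake is a p-value and confidence interval labelled as the gain from switching that could have the wrong sign. There is also a pre-specification gap: different programmers could choose different contrasts, and SAP 3.5.4 and 7.7 allow interim OLE analyses after the Main Study has been unblinded.

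**Working it through.** The documents give no figure for this contrast, so there is none to reproduce. The planning inputs borrowed below are consistent with the stated power: 186 per arm, difference 0.7 and SD 1.9 give 0.944 against the stated 94%.

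Inputs:
- Annual TFC decline r: 0.8 to 1.2 points for TFC 7 to 13 (Protocol 8.1.1).
- Rollover week T: 65 to 78 (SAP 3.1).
- Design effect: 0.7 points at Week 65 (SAP 3.3).
- Assumptions: linear decline without an effective drug; the design effect accrues linearly, 0.7/65 per week.

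**Same-week contrast.** Let m(t) be mean TFC at week t from randomization. Then

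[m(T+w) - m(0)] - [m(w) - m(0)] = [m(T) - m(0)] + {[m(T+w) - m(T)] - [m(w) - m(0)]}.

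The first bracket on the right is the decline on placebo before rollover. The braces hold the within-period comparison. For an inert drug the braces are 0 and the contrast is -r × T/52 at every w. The accrued design effect adds 0.7 × 26/65 = 0.28 at week 26 and 0.7 × 52/65 = 0.56 at week 52.

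| r per year | T | Inert drug | Design effect, w = 26 | Design effect, w = 52 |
|---|---|---|---|---|
| 0.8 | 65 | -1.00 | -0.72 | -0.44 |
| 0.8 | 78 | -1.20 | -0.92 | -0.64 |
| 1.2 | 65 | -1.50 | -1.22 | -0.94 |
| 1.2 | 78 | -1.80 | -1.52 | -1.24 |

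**Within-period contrast** (the braces alone): 0 for an inert drug at every r, T and w above; +0.28 at week 26 and +0.56 at week 52 with the design effect.

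**Simulation check.** Complete data, 200 participants, 2,000 runs, r = 1.0, T = 78, inert drug: the same-week contrast averaged -1.50 at both weeks and the within-period contrast 0.00.

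**Precision, as illustration.** The number of switchers is not known; the planning figures give 240 × 0.775 = 186. At T = 65 the same-week difference spans 65 weeks, so take the planning SD of 1.9 for a 65-week change. SE = 1.9/√186 = 0.139, and an estimate of -1.00 has a 95% CI of -1.00 ± 1.96 × 0.139, or -1.27 to -0.73. An inert drug would look clearly harmful.

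**Starting point of the OLE.** According to the Protocol 1.3.2 footnotes, the first OLE visit "is the same as Main Study V8 (or V7/W65 for the last group of participants in the Main Study"), and SAP 3.1 also allows an end-of-study visit between those weeks. If Week 65 were used as the anchor for someone who rolls over at Week 78, 13 weeks of placebo decline would remain: -r × 13/52 = -0.20 to -0.30.

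**Weeks that can be paired.** The OLE schedule runs to "OLE Wk 52 & every 26 wks thereafter". On a 26-week grid the Main Study has counterparts at Weeks 26 and 52, and at Week 78 only for those who reach it.

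**The case against.** The strongest reply is that the SAP never says the contrast is OLE week w minus Main Study week w. Its purpose clause speaks of a gain after switching, which a within-period contrast would estimate and the same-week contrast would not. That contrast can be built with the data and model already planned, and the OLE Baseline it needs is already defined. A reader might therefore infer from the figures above that the SAP prescribes a biased analysis. The documents do not support that: the contrast is unstated, and the -1.0 to -1.8 holds only for one reading. What survives is that the stated response and visit numbering lead to that reading, and nothing operational points to the other.

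The reach is also small. SAP 3.5.3 bases the submission on Main Study data, with OLE results to follow. The error runs against pridopidine, so it could not create a false claim of benefit. A reader might infer that the trial's efficacy conclusions are at risk; they are not.

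Two cautions on size also stand. The 0.7 is a Week 65 figure, so it is scaled to weeks 26 and 52 above rather than applied in full. And re-basing does not give an unbiased drug effect. Protocol 8.1.1 says decline slows to 0.2 to 0.3 points per year in Stage 3. If a share p of switchers slowed from r to s on entering the OLE, an inert drug would show p × (r - s) × w/52. The documents give no such share; at an assumed 25% this is +0.06 to +0.13 at week 26 and +0.13 to +0.25 at week 52, in the drug's favour. Open-label rating adds a further period difference that cannot be quantified from the documents.

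**Conclusion.** The point holds as an unspecified contrast whose most direct reading fails its stated purpose. On that reading the analysis would return -1.0 to -1.8 points for an inert drug. With the design effect it would return about -0.7 to -1.5 at OLE week 26 and -0.4 to -1.2 at week 52. These sizes rest on linear decline, on the protocol's 0.8 to 1.2 points per year applying to those who roll over, and on linear accrual of the effect. The sign is the same throughout the range examined.

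The point concerns one supportive model outside the testing hierarchy. The OLE responder, Kaplan-Meier and Cox analyses compare the two randomized groups over the same elapsed time and do not share the problem. It should be corrected because an inferential result will be reported under a label that it may not match.

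**What to change.** In SAP 7.7 only:

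- Define the contrast at week w as (OLE week w minus OLE Baseline) minus (Main Study week w minus Main Study Baseline), with OLE Baseline as in 5.5.1.2. Each participant is then anchored at the actual end-of-study visit, not at a fixed Week 65.
- Report it at weeks 26 and 52.
- Keep Main Study Baseline TFC as the covariate. In simulations under assumed variances, replacing it with an uncentred period-specific baseline with a common slope gave about -0.06 to -0.23 at week 26 for an inert drug.
- State that treatment and period remain confounded in this single group, through open-label rating and through slowing of decline in Stage 3 that would favour the drug, so the result is supportive only.

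The cost is a few sentences, with the same data and software. Protocol 9.4.6 can stand: it specifies no contrast, and Protocol 9 and SAP 1 both let the SAP prevail, so no protocol amendment is needed. SAP 5 provides an addendum for changes before lock and unblinding. In any case, the contrast should be fixed before any OLE efficacy data are analysed. The price is that the residual confounding stays and has to be stated beside the result.
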